delivered by the research team. The first session will focus on the physical literacy of older adults and the second session will focus on how to lead functional fitness training under the FITT principle (Frequency, Intensity, Time, Type; and how they relate to cardio, strength, stretching and injury prevention) for older adults. A further important issue that will be mentioned is related to ensuring the safety of older adults during the whole intervention, which will emphasize the process-oriented outcomes and encouragement to participation, rather than the product oriented assessments. Meanwhile, the main goal of functional training is to improve the range of joint motion, increase muscle strength and flexibility, and boost blood circulation in a safe and acceptable manner. Therefore, symmetry training together with cardiovascular training is the core of the training program. Examples of the main training activities include cardio-fullbody exercises (e.g. move adherence to the music training, including running, jogging, dancing movements, etc.), upper body exercises (e.g. bench press, rowing and lifting), lower body exercises (e.g. squatting and lateral hurdle jumps with tap-sensitive pods) and sensory integrative training (e.g. shooting training with an electronic sensory wall).

Part 2: Mastering physical literacy class (MPLC)

A 30-minute MPLC program will be conducted by experienced elderly health and fitness instructors after WBFFT. This MPLC program aims to enhance the knowledge and understanding of physical literacy. Referring to the newly developed consensus statement (10), the MPLC includes the following five domains related to the relationship with movement and physical activity throughout life:

- i. Why physical literacy matters – improves health, well-being and quality of life.
- ii. Understanding physical literacy – value, enjoy and engage in physical activity for life.
- iii. Everyone's physical literacy is different – their individual needs and experiences of movement and physical activity.
- iv. Building physical literacy – think, feel, move and connect with others.
- v. How experience affects physical literacy – people, places and spaces around us.

Part 3: Daily-based reflective writing (DBRW)

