In this proposed study, peer-support groups with buddy members will be arranged in each daycare center. Three pairs of buddies and hence about 6 participants will be formed per group. A total of 6 buddy pairs and 2 groups will be formed per daycare center. Buddy peers will encourage each other to do functional exercises regularly or to perform functional exercises together. The time and place for the practice will be decided among buddy members. A member in each group will be nominated as the leader to assist in the liaison and coordination of group activities. The group will perform weekly group-based functional exercises, and the time and place for the practice will be decided among group members. The group will be encouraged to hold monthly gatherings with their fitness instructor in order to strengthen social support.

Study design

A two-arm cluster randomized controlled trial will be employed in this proposed study (see details in Fig 1). According to the Social Welfare Department of Hong Kong, there are 98 daycare centers for the elderly in 2023 (14). Daycare centers for the elderly located in 3 regions in Hong Kong will be invited to participate in the intervention. The PLBI will be conducted for twelve weeks.

Sample size and participants

The required sample size is calculated based on the hypothesized effect sizes, and the likely rates of participant drop-out for the outcomes. The estimated sample size is 198 with an effect size of 0.25, α of 0.05 and power of 0.95 (15). With the anticipation of a 20% participant drop-out rate, this led to a required number of 120 participants per group. Therefore, 10 daycare centers for the elderly in Hong Kong will be invited to participate in this study.

Physical literacy-based intervention group (PLBI)

Inclusion criteria will be: 1) those aged 65 to 74 years old who are registered in a daycare center/unit for the elderly in Hong Kong, 2) the ability to walk eight meters without assistance (16), and 3) able to read and write. Exclusion criteria will include 1) neurological disease which impairs mobility, cardiovascular disease which results in shortness of breath or angina on walking up one flight of stairs, and 2) cognitive impairment. Participants' cognitive function will be screened by the Chinese Mini-Mental State Examination (17, 18), and those who score below 24 will be excluded.

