Accelerometers (Actigraph wGT3X-BT) will be used to measure the physical activity engagement levels of participants, and are categorized as sedentary, light, moderate and vigorous. Data was collected in 60 s epochs to account for elderly people's natural activity levels, as it was shown to present the most acceptable classification accuracy for accelerometer use among older adults (20). The cut-points developed by Aguilar-Farías et al. was applied to identifying intensity levels (20). Participants will wear accelerometers at the waist to measure their physical activity engagement levels for at least 8 hours per day, for seven consecutive days.

Self-report measures (secondary outcomes)

Demographic information

Demographic information including age, gender, BMI (height and weight), education, and socio-economic status will be included in the starting part of the questionnaire set, in order to acquire personal characteristics for further analysis.

Daily behavior

International Physical Activity Questionnaire – short form is the short version of the International Physical Activity Questionnaire used to measure self-reported physical activity levels. They will be required to report on the total duration of different types of physical activity which lasted at least 10 uninterrupted minutes in the last 7 days.

Example item included: During the last 7 days, how many days did you do vigorous physical activities?

Knowledge and understanding

Montreal Cognitive Assessment (MoCA) is a 30-question brief and sensitive test used for detecting Alzheimer's disease and measuring executive functions and multiple cognitive domains. It is widely adopted for older adults and will be used to assess knowledge and understanding of physical literacy among the elderly. MoCA-B is a revised MoCA test. The Chinese Version of MoCA-B tests nine cognitive domains (executive function, language, orientation, calculation, conceptual thinking, memory, visual perception, attention, and concentration), and has been reported as a reliable cognitive screening test across all education levels in Chinese elderly adults (21), with high acceptance and good reliability.

Physical literacy

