The perceived Physical Literacy Instrument (PPLI) is a 9-item instrument which is used to measure the perceived physical literacy of different individuals (22, 23). Three subscales are "sense of self and self-confidence", "self-expression and communication with others" and "knowledge and understanding" which were identified as key attributes of physical literacy (4). Participants responded to the instrument on a 1 to 5 Likert scale (1 = strongly disagree and 5 = strongly agree). Sum et al. (22) confirmed that the three-factor validity (RMSEA = 0.08; CFI = 0.94 and SRMR = 0.04) and convergent validity (CR = 0.72 - 0.78; AVE = 0.43 - 0.54) of the PPLI was satisfactory.

Motivation and confidence

Perceived Well-being Scale (PWB) contains 14 items with 7 points which will be used to measure participants' motivation and confidence (24). It is a short and convenient measure for use with community-based and institutionalized elderly. Example items include: (a) I am often bored (psychological well-being); (b) I am in good shape physically (physical wellbeing). The validity of PWB is sufficiently high to justify being used with the elderly, in particular in longitudinal and intervention studies.

Buddy Peers Support

A 5-item Friend Support for Exercise Habit Subscale of the validated Social Support for Diet and Exercise Behavior Scale will be used (25). Five questions are "exercise with me", "offered to exercise with me", "gave me reminder to exercise", "gave me encouragement to stick with my exercise program", and "changed their schedule so we could exercise together". Participants responded to the instrument on a 1 (none) to 5 (very often) Likert scale. Sallis et al. (25) confirmed that the sub-scales are with high acceptance and good reliability.

Data analysis

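### Two secondary outcomes carry labels that the plan's own descriptions do not support: MoCA-B as physical-literacy knowledge, and the Perceived Well-being Scale as motivation and confidence

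*Combined protocol and SAP*

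**What the plan says.** The following parts of the combined protocol and SAP bear on this point.

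- **Part 2, Mastering physical literacy class (MPLC).** "This MPLC program aims to enhance the knowledge and understanding of physical literacy". The five topics listed are why physical literacy matters, what it is, how it differs between people, how it is built, and how experience shapes it.
- **Self-report measures, Knowledge and understanding.** The MoCA "will be used to assess knowledge and understanding of physical literacy among the elderly". It is described there as a "brief and sensitive test used for detecting Alzheimer's disease and measuring executive functions and multiple cognitive domains". The Chinese MoCA-B is said to cover nine cognitive domains, and it "has been reported as a reliable cognitive screening test across all education levels in Chinese elderly adults".
- **Self-report measures, Motivation and confidence.** The PWB "contains 14 items with 7 points which will be used to measure participants' motivation and confidence". Of its two example items, one is tagged psychological well-being and the other physical well-being.
- **Self-report measures, Physical literacy.** The PPLI has nine items rated from 1 to 5. Its three subscales are *sense of self and self-confidence*, *self-expression and communication with others*, and *knowledge and understanding*.
- **Data analysis.** The group-by-time interaction, which the plan calls the intervention effect, is examined for primary and secondary outcomes alike. No PPLI subscale is named as the outcome for the knowledge or confidence domain.

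**The concern.** The opening of Outcome measures says that the instruments were chosen so that together they cover the domains of physical literacy. The heading above each instrument therefore tells the reader what a result on it will mean. For two headings, the instrument described underneath measures something else.

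The misreading could go in either direction. If the class teaches its content well and MoCA-B does not move, the plan's label turns that into a failure to improve knowledge. If MoCA-B does move, for instance because of the exercise, the label turns a cognitive change into a knowledge gain. The PWB has the same weakness: one example item asks about being in good physical shape, which twice-weekly fitness training could shift directly, and the plan would file that under motivation and confidence.

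**Working it through.** The plan gives no figure on this point and the conclusion depends on none, so the check is a comparison of what each instrument is assigned to measure with what the plan says it measures.

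| | Knowledge domain | Motivation and confidence domain |
|---|---|---|
| Instrument assigned | MoCA / MoCA-B | PWB |
| What the plan says it measures | Alzheimer's detection, executive function, nine cognitive domains | Psychological and physical well-being (example items) |
| Support given | Reliable as a cognitive screen; the cited paper's title concerns screening for mild cognitive impairment | Valid enough for use with the elderly, including intervention studies; motivation and confidence are not mentioned |
| PPLI subscale with a matching name | *Knowledge and understanding* | *Sense of self and self-confidence* (confidence only) |

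**Step 1. Does MoCA-B match what the class teaches?** The nine domains are executive function, language, orientation, calculation, conceptual thinking, memory, visual perception, attention and concentration. None is physical-literacy content. A participant could learn all five class topics and gain no MoCA-B point.

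**Step 2. Does the PWB match its heading?** Its name, its example items and the title of its cited source all refer to well-being. Nothing in the plan links a PWB score to motivation or confidence.

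**Step 3. Does another section repair this?** Data analysis puts all primary and secondary outcomes into the same three-level model. It plans Cronbach's alpha for the questionnaire sub-scales, but does not redirect the two domain conclusions to PPLI subscales.

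**Step 4. How far can the PPLI stand in?**
- It covers knowledge and confidence by name. It has no subscale named for motivation.
- It records perceived physical literacy by self-rating, so it does not test knowledge.
- Nine items over three subscales is 9 / 3 = 3 items per subscale on average, and the reported average variance extracted runs from 0.43 to 0.54.
- The titles of its two cited validation papers refer to adolescents and to physical education teachers. Reference 18 has a title about perceived physical literacy among older adults in Hong Kong day care centers. The plan cites it for the choice of physical competence test and the cognitive screen, not as validation of the PPLI.

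**The case against.** The strongest defence has three parts.

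1. *Physical literacy has cognitive and psychological sides.* The introduction cites a standard with physical, psychological, social and cognitive domains, so MoCA-B and the PWB might represent the cognitive and psychological ones. That is a good reason to collect both scales. It does not support the labels, because the plan assigns MoCA-B to knowledge of physical literacy rather than to cognition, and the PWB to motivation and confidence rather than to well-being.
2. *The PPLI is collected anyway.* This is true, and it makes the remedy cheap. But the plan still ties the domain results to the other two instruments.
3. *MoCA-B is a performance test, while the PPLI is self-rated by people who know whether they attended the class.* This stands. Self-rated knowledge is open to expectation effects, so the PPLI subscale has to be reported as perceived knowledge. It does not make MoCA-B a test of the class content.

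A reader might also infer more than the documents support:

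- *That the trial cannot answer its main question.* The Short Physical Performance Battery, accelerometry and the overall PPLI score are untouched.
- *That the PPLI can replace both instruments in full.* It cannot do so for motivation, and for knowledge it offers only self-perception.
- *That the loss of power can be calculated by scaling a knowledge gain by its correlation with MoCA-B.* The documents give no such correlation. A cross-sectional correlation also does not determine how much of a treatment effect on one variable appears on another. The stated power of 0.95 is for an effect size of 0.25 with no outcome named, so it is no benchmark for MoCA-B.
- *That the entry screen removes MoCA-B's room to move.* The screen is the Chinese Mini-Mental State Examination, where "those who score below 24 will be excluded". Some narrowing of the cognitive range is plausible, but this is a different instrument and no MoCA-B distribution is given, so its size is unknown.

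**Conclusion.** The concern holds for two secondary domains. On the plan's own descriptions, MoCA-B measures cognition and the PWB measures well-being. Neither a group-by-time effect nor a null on them supports a conclusion about physical-literacy knowledge, or about motivation and confidence.

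The conclusion rests on two things: the plan's descriptions of the instruments, taken at face value, and the assumption that the domain headings will carry through to the report. The plan has no reporting rule, so the second is an inference from the headings. No numerical magnitude is claimed. The mismatch is one of labelling and interpretation, and it should be settled before results by group are seen.

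**What to change.** Amend Self-report measures and Data analysis as follows.

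1. Rename the MoCA-B outcome cognitive function and the PWB outcome perceived well-being. State that no knowledge, motivation or confidence conclusion will be drawn from them.
2. Pre-specify the PPLI subscale *knowledge and understanding* as the outcome for perceived knowledge, and *sense of self and self-confidence* as the outcome for self-confidence, both in the existing three-level model.
3. State the limits of those subscales: they are short, they are self-rated by participants who know whether they attended the class, and the cited validation papers have titles concerning adolescents and physical education teachers. The planned alpha, with its 0.7 cut-off, will describe internal consistency in this sample but will not establish validity.
4. Drop the claim to measure motivation, because no PPLI subscale is named for it.

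The cost is wording only: no new data and no change to the model. The downside is that motivation is no longer claimed as measured, and knowledge is assessed only as participants perceive it.

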Assessment or charting progress in relation to physical literacy is essential, as this will help clarify policymakers' understanding of the concept as well as individuals' appreciation of their physical literacy journeys, and how they might develop physical literacy through a lifespan (2). Physical literacy is an individualized personal journey so any assessment trying to support this journey should be relative to the individual and their progress and must reflect the changes over time (19). Therefore, this study will adopt both objective and self-reported measures to cover the elements and domains of physical literacy. Participants will be evaluated at baseline (week 0), post-intervention (week 12), and at a 6-week follow-up (week 18). All of them will be conducted at daycare centers for the elderly. The self-reported measurements will be administered by research assistants while the objective measurements will be performed by certified physical fitness assessors and health professionals who are blinded to the randomization for avoiding bias.

Objective measure (primary outcomes)

Physical competence

The Short Physical Performance Battery (SPPB) will be used to measure the physical competence within the physical literacy of older adults (16). Huang et al. (18) suggested using a combined and comprehensive kit of assessment tools to measure physical competence, and the SPPB was reported to be able to measure complex capabilities with excellent test-retest reliability, especially in community-dwelling older adults. It is a group of measures that combines the results of the gait speed, chair stand and balance tests, which consist of balance, a timed eight-foot walk and chair stands. The scores range from zero (worst performance) to 12 (best performance). It has been used as a predictive tool for possible disability and can aid in monitoring function in older people. The reliability of SPPB has been reported as $ICC = 0.75 - 0.89$ for all measures.

Daily behavior

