SPSS version 28 for Windows will be used for data analysis. Internal consistency reliability coefficients (Cronbach alpha) will be calculated for all sub-scales within the psychometric questionnaires. A cut-off score of 0.7 will be used to determine acceptable reliability. Descriptive statistics (means and standard deviations) will be calculated for participants' primary and secondary outcomes (objective and self-reported) at three-time points. Multilevel modeling methods were used to account for the clustered nature of the data. Specifically, we used three-level (time within older adults within daycare center) regression analyses to examine the effects of group (experimental vs control), time (baseline, post-test and follow-up), and the group-time interaction (i.e., "intervention effect") on the primary and secondary outcomes. Covariates such as age, gender, BMI, education, and socioeconomic status will be included in the analysis. Bonferroni post hoc analyses will be conducted to determine contributing factors to the significance of F values, and the confidence level will be set at 95% to maintain statistical reliability for all the analyses.

Evaluation plan

At post-intervention, in-depth interviews of a group of 8 - 12 participants will be conducted to explore their experiences in participating in the intervention, the level of satisfaction with the intervention, and the barriers and expediter in performing the PLBI as instructed. DBRW will also be material for evaluation analysis. The reasons why participants dropped out of the study will also be recorded. Additionally, participants will be invited to fill in a process evaluation survey which assesses their level of involvement and level of satisfaction with the intervention.

Reference

1. Morgan K. Applying the TARGET Pedagogical Principles in Physical Education to Enhance Students' Physical Literacy. *Journal of Physical Education, Recreation & Dance*. 2019;90(1):9-14.

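### The analysis model is defined only by its nesting. Fitted as a person intercept it imposes one correlation on visits at weeks 0, 12 and 18 and, if correlation falls with the gap, understates the week-18 standard error by about 10–16%.

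*Combined protocol and SAP*

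**What the plan says.** The Data analysis section gives the reason for the model as clustering: "Multilevel modeling methods were used to account for the clustered nature of the data". The model itself is described as "we used three-level (time within older adults within daycare center) regression analyses", with fixed effects for group, "time (baseline, post-test and follow-up), and the group-time interaction", and covariates. The section equates the interaction with the intervention effect. Follow-up tests are described as "Bonferroni post hoc analyses will be conducted to determine contributing factors to the significance of F values", without naming the pairs to be compared. On software: "SPSS version 28 for Windows will be used for data analysis". No procedure, random slope, residual covariance type or within-person correlation is stated.

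The Outcome measures section fixes the visit times: "Participants will be evaluated at baseline (week 0), post-intervention (week 12), and at a 6-week follow-up (week 18". The gaps are therefore 12 weeks (0 to 12), 6 weeks (12 to 18) and 18 weeks (0 to 18).

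**The concern.** The intervention effect is a difference between arms in within-person change, so its standard error depends directly on how the model treats correlation between a person's visits. When only the nesting is given, the ordinary implementation is a random intercept at each level plus independent residuals. That implies one common correlation for all three pairs of visits and one pooled residual variance for every change contrast.

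Weeks 12 and 18 are the closest pair in time and both follow the programme. Weeks 0 and 18 are the furthest apart and span it. If the 12–18 correlation is the highest and the 0–18 correlation the lowest, the pooled error is too small for the 0–18 contrast and too large for the 12–18 contrast. The confidence interval for the effect at follow-up would be too narrow, and that for the comparison of week 18 with week 12 too wide.

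**Working it through.** **Inputs from the documents.** Visits at weeks 0, 12 and 18, the three-level nesting, the group-by-time interaction as the effect, and Bonferroni follow-up tests. There is no planned correlation or standard error to reproduce. The sample-size statement ("The estimated sample size is 198 with an effect size of 0.25, α of 0.05 and power of 0.95 (15") names neither the test nor a within-person correlation. Its total of 198 is not recovered from the stated inputs: a two-group ANOVA with f = 0.25 needs 210. Nothing below depends on it, because the number of participants cancels from the ratios.

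**Inputs assumed.** All correlations. The only reliability figure for a primary outcome, the SPPB ICC of 0.75–0.89, is not stated to be a correlation over 6, 12 or 18 weeks.

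**Formula.** Take complete, balanced data with equal variance σ² at each visit. The true variance of one person's change between two visits is 2σ²(1 − ρ of that pair). The person-intercept model uses 2σ²(1 − mean ρ) for every pair. Hence

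model SE / true SE = √[(1 − mean ρ) / (1 − ρ of the pair)].

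A centre intercept cancels from change contrasts and does not alter this.

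**Worked example**, correlations 0.60 (0–12), 0.55 (0–18), 0.80 (12–18). The mean is 1.95/3 = 0.65.

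- 0–12: √(0.35/0.40) = 0.935
- 0–18: √(0.35/0.45) = 0.882
- 12–18: √(0.35/0.20) = 1.323

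**All four assumed sets:**

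| ρ 0–12 / 0–18 / 12–18 | Mean ρ | Ratio 0–12 | Ratio 0–18 | Ratio 12–18 |
|---|---|---|---|---|
| 0.60 / 0.55 / 0.80 | 0.650 | 0.935 | 0.882 | 1.323 |
| 0.70 / 0.65 / 0.80 | 0.717 | 0.972 | 0.900 | 1.190 |
| 0.72 / 0.61 / 0.85 | 0.727 | 0.988 | 0.837 | 1.350 |
| 0.75 / 0.65 / 0.85 | 0.750 | 1.000 | 0.845 | 1.291 |
| all equal | – | 1.000 | 1.000 | 1.000 |

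The week-18 standard error is thus 10–16% too small and the 12-versus-18 standard error 19–35% too large.

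**Unadjusted type I error at week 18.** By normal approximation this is 2[1 − Φ(1.96 × ratio)]. A ratio of 0.900 gives a cut-off of 1.764 and 7.8%. A ratio of 0.837 gives 1.641 and 10.1%. Simulation of null trials with 96 per arm gives 7.7–9.7% across the four sets, against about 5% with an unstructured covariance.

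**Week 12.** The 12-week gap is the middle one, so under decay by gap its correlation lies near the average. If correlation falls exponentially (6-week ρ from 0.60 to 0.95) the ratio is 0.975–0.996. If it falls linearly the ratio is exactly 1.000. If it falls faster late (0.80/0.75/0.60 at 6/12/18 weeks) the ratio is 1.065, so the standard error is too large. Only the first assumed set, with a marked jump in the 12–18 correlation, gives as much as 6% too small.

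**After Bonferroni.** Over all three pairs, simulated family-wise error is 4.7–5.3%, but it is unevenly spread. In the first set the week-12 and week-18 contrasts reject in 2.6% and 3.5% of null trials, against a nominal 5%/3 = 1.7% each. If only the two baseline contrasts are corrected, family-wise error is 6.2–7.0%. The overall two-degree-of-freedom interaction test rejects in about 5.9% under the first set.

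**The case against.** Three stronger statements are tempting, and the documents support none of them.

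- **That the plan commits to one intercept per person.** It states only the nesting. Random slopes or a structured residual covariance are compatible with the same words, and SPSS MIXED can fit them. The person intercept is the ordinary implementation and a fair inference, but not a stated fact. If it is not what is intended, the error term of the main effect is left unspecified, and the same sentence in the plan is needed.
- **That the week-12 standard error is also too small.** Unequal spacing alone does not produce this. A further mechanism is possible: people may respond differently to the programme, and weeks 12 and 18 share that response while baseline does not. This applies only to the intervention arm, because controls receive the programme after all data are collected. An assumed response variance of 0.1–0.2 (total variance 1) in that arm moves the week-12 ratio under linear decay from 1.000 to 0.985–0.972, which is modest. Uneven retention of gains after week 12 could work the other way.
- **That type I error of the planned procedure exceeds 5%.** The 8–10% is for the unadjusted week-18 contrast. Bonferroni over three pairs holds family-wise error near 5%. An excess arises if only the two baseline contrasts are corrected, and the plan does not say which pairs it means.

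It can also be said that centre-level variation in change may matter more. With an assumed centre-by-time variance of 0.01 left unmodelled (total SD about 1, ρ 0.75), all three standard errors fall to about 0.73 of the truth. That stands, but it is a separate issue. With such variation modelled (ICC 0.05, centre autocorrelation 0.8), the first correlation set still gave type I error of 6.0% at week 12 and 7.1% at week 18.

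**Conclusion.** The point holds conditionally. If the model is fitted with a person intercept and independent residuals, and within-person correlation falls with the gap, the baseline-to-week-18 effect gets a standard error about 10–16% too small, and week 12 versus week 18 one about 19–35% too large. The baseline-to-week-12 effect is about right, or at most modestly affected. Three-pair Bonferroni contains the family-wise error, but it does not correct the imbalance between contrasts or the width of the intervals.

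The sizes rest on assumed correlations, complete data and equal variances. With equal correlations there is no error. This is a worthwhile, inexpensive improvement to the main analysis rather than a flaw that invalidates it.

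**What to change.** In the Data analysis section, specify an unstructured residual covariance over the three visits within participant, in place of the person intercept. In SPSS MIXED this is REPEATED by visit, SUBJECT = participant, COVTYPE(UN). Keep the centre random effects. Name a simpler fallback structure in case the model does not converge. Take the week-12 and week-18 contrasts from this model, and state which pairs the Bonferroni correction covers.

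The cost is a sentence or two in the plan and one line of syntax. An unstructured 3 × 3 covariance has six parameters and a person intercept with residual has two, so four are added. About 200 participants can easily support them, and little is lost if the correlations turn out equal. The change does not deal with centre-level variation in change, which needs its own provision.
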